6.1.5 Visit Windows

For safety analyses (laboratory and vital signs data) and efficacy analyses, by-visit summaries and analyses will analyze assessments by visit as designated on the CRF; visit remapping based on study day to an analysis visit window won't be applied. Unscheduled visits will be excluded from by-visit summaries and analyses. The Early Discontinuation

GRIFOLS	Bioscience Industrial Group	Number	IG1601	Version	2.0	Status	Effective	Effective Date	09-Sep-2024	Page	20 of 52
		IG1601	Statistical Analysis Plan								

visit will be summarized as a separate visit, without adjusting for the timing of assessments for subjects that discontinue early.

For the analyses of exploratory endpoints, the early discontinuation visit will be mapped to an assessment visit. The mapping will be based on the timing of a subject's assessment visit, relative to their Study Day 1. A detailed list of the parameters and the mapping rules to be applied is provided in [Appendix 4](#).

For cases where multiple assessments are recorded for a parameter within a single visit window, the following rules will be applied for each parameter:

- If 2 or more assessments are mapped to the same visit window, then the non-missing assessment closest to the scheduled visit target day will be used in the analysis.
- If 2 assessments are equidistant from the visit target day, the later non-missing observation will be used in the analysis.

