8.4 Treatment Compliance for Albutein 20% Administration

Treatment compliance, infusion compliance, and overall compliance will be listed and summarized for the SMT + Albutein 20% group specific to the Albutein study drug treatment. In addition, the number and percentage of subjects with Albutein compliance <80%, 80% to \leq 120%, and >120% will be presented. Infusion compliance will be calculated as (number of actual infusions / number of infusions expected or planned) *100. For subjects that complete the study, the number of infusions expected is 37. For subjects who drop out from the study early, the number of infusions expected or planned will be calculated as [(date of end of study visit – date of randomization) / 10 + 1].

Treatment compliance will be calculated as (total volume infused / total volume prepared)*100. Missing visits will be excluded in the calculation.

Overall compliance will be calculated as (treatment compliance * infusion compliance)/100.

Treatment compliance for the SMT alone group is not applicable for any Albutein study drug compliance assessments.

Effective Date	09-Sep-2024
Page	27 of 52

Number	IG1601 Statistical Analysis Plan

GRIFOLS	Bioscience Industrial Group

9 Efficacy Analysis

All efficacy listings and summaries will be based on the ITT population. In addition, the primary and secondary efficacy summaries and analyses will be repeated for the PP population.

For the purposes of defining the analysis period for each of the efficacy analysis timepoints the following will be applied:

Analysis Timepoint	Analysis Period	Cut-Off Date
1 Year	362 Days	Randomization Date + 361 Days
6 Months	182 Days	Randomization Date + 181 Days
3 Months	92 Days	Randomization Date + 91 Days

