9.3.1 Incidence of ACLF at 3, 6 and 12 Months

ACLF is evaluated monthly through Month 12 and will be listed.

The number and percentage of subjects with at least one occurrence of ACLF from Month 1 through Month 3 will be presented by treatment, and treatment differences will be analyzed by the Chi-square test. Month 1 is inclusive of the occurrences reported at the Day 11 and Month 1 scheduled visits.

The same summary and analysis will be performed for the ACLF evaluations occurring from Month 1 through Month 3, from Month 1 through Month 6, and for all ACLF evaluations occurring from Month 1 through Month 12.

GRIFOLS	Number	BIG-CL-SP-000319	Version	2.0	Status	Effective	Effective Date	09-Sep-2024	Page	34 of 52
	IG1601	Statistical Analysis Plan								

In addition, the ACLF evaluations will be summarized by treatment group for each visit, reporting number and percentage of subjects reporting ACLF and the ACLF grade by visit.

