Appendix 4 – Visit Mapping for early discontinuation visit

Table 1: Scheduled Visits and Analysis Visit Windows for ALCF, CLIF-C OF Score and Sub Scores, CLIF-C ACLF Score, CLIF-C AD Score, MELD Score, Child Pugh Score, Child Pugh Sub Score, Child Pugh Class, Serum Albumin Concentration

Analysis Period	Scheduled Time Point	Analysis Visit (label on output)	Target Time Point (Day*)	Analysis Visit Window (Day)*
Baseline	Day 1	Baseline	1	<=1
	Day 11	Day 11	11	[2 to 21]
	Day 31 (Month 1)	Day 31 (Month 1)	31	[22 to 46]
			61	[47 to 76]
	Day 61 (Month 2)	Day 61 (Month 2)		
	Day 91 (Month 3)	Day 91 (Month 3)	91	[77 to 106]
	Day 121 (Month 4)	Day 121 (Month 4)	121	[107 to 136]
	Day 151 (Month 5)	Day 151 (Month 5)	151	[137 to 166]
	Day 181 (Month 6)	Day 181 (Month 6)	181	[167 to 196]
	Day 211 (Month 7)	Day 211 (Month 7)	211	[197 to 226]
	Day 241 (Month 8)	Day 241 (Month 8)	241	[227 to 256]

	Day 271 ((Month 9)	Day 271 ((Month 9)	271	[257 to 286]
	Day 301 (Month 10)	Day 301 (Month 10)	301	[287 to 316]
	Day 331 (Month 11)	Day 331 (Month 11)	331	[317 to 346]
	Day 361 (Month 12)	Day 361 (Month 12)	361	[347 to 376]

*Relative to Study Day 1.

Note: For Serum Albumin Concentration this is the Day 1 pre-dose visit

Table 2: Scheduled Visits and Analysis Visit Windows for Albumin Functional Capacity in Serum (Albumin Binding Capacity)

Analysis Period	Scheduled Time Point	Analysis Visit (label on output)	Target Time Point (Day*)	Analysis Visit Window (Day)*
Baseline	Day 1	Baseline	1	<=1
	Day 11	Day 11	11	[2 to 21]
	Day 31 (Month 1)	Day 31 (Month 1)	31	[22 to 46]
			61	[47 to 76]
	Day 61 (Month 2)	Day 61 (Month 2)		
	Day 91 (Month 3)	Day 91 (Month 3)	91	[77 to 106]
	Day 121 (Month 4)	Day 121 (Month 4)	121	[107 to 136]
	Day 151 (Month 5)	Day 151 (Month 5)	151	[137 to 166]
	Day 181 (Month 6)	Day 181 (Month 6)	181	[167 to 196]
	Day 211 (Month 7)	Day 211 (Month 7)	211	[197 to 226]
	Day 241 (Month 8)	Day 241 (Month 8)	241	[227 to 256]
	Day 271 ((Month 9)	Day 271 ((Month 9)	271	[257 to 286]
	Day 301 (Month 10)	Day 301 (Month 10)	301	[287 to 316]
	Day 331 (Month 11)	Day 331 (Month 11)	331	[317 to 346]
	Day 361 (Month 12)	Day 361 (Month 12)	361	[347 to 376]

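### SAP 9.3.1 counts any ACLF occurrence, but the one-value-per-window rule in SAP 6.1.5, read literally, can drop ACLF first seen at an early discontinuation visit

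*SAP*

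**What the plan says.** **Endpoint.** SAP 9.3.1 plans this summary: "The number and percentage of subjects with at least one occurrence of ACLF from Month 1 through Month 3 will be presented by treatment", with a chi-square test. It repeats the analysis through Month 6 and "for all ACLF evaluations occurring from Month 1 through Month 12". Month 1 includes findings at both the Day 11 and Month 1 visits. ACLF and its grade are also summarized separately by visit, and all evaluations are listed.

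**Visit handling.** SAP 6.1.5 first says that analyses use the visit as labelled on the CRF and that the ED visit stands as a separate visit. It then makes a specific provision: "For the analyses of exploratory endpoints, the early discontinuation visit will be mapped to an assessment visit". For each parameter, when a window holds more than one assessment, "then the non-missing assessment closest to the scheduled visit target day will be used in the analysis"; the later one is used in a tie.

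**Scope.** Appendix 4 Table 1 is headed "Scheduled Visits and Analysis Visit Windows for ALCF, CLIF-C OF Score and Sub Scores", and the list continues with other scores. The first term is evidently ACLF. The Month 3 window is Days 77 to 106 around Day 91.

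**What the ED visit contains.** SAP 5.2.5 has early discontinuers complete the Month 12 assessments, which include the ACLF grade (SAP Appendix 1). After that, only transplantation, survival and cause of death are collected (SAP 5.2.7).

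**The concern.** A nearest-to-target rule suits a score that needs one value per visit. It does not suit an endpoint that asks whether something ever happened, because a negative result close to the target day can displace a later positive one. The displaced ED result is the subject's last ACLF assessment, and no later assessment can recover the event.

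At stake is the classification of some early discontinuers in the ACLF comparison at 3, 6 and 12 months. Because the trial is open-label, a difference between arms in discontinuation would carry some of that misclassification into the treatment comparison.

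**Working it through.** The documents give no figure for this point, so there is none to reproduce. The check applies the rule to every possible ED day.

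**Inputs**
- Windows: Appendix 4 Table 1 (Day 11: Days 2–21; Day 31: Days 22–46; then target −14 to +15).
- Scheduled visits at target ±2 days: SAP 5.2.3.
- Dropout of 20% of 410, that is 82 subjects: SAP 6.2. Used only for sizing.
- Assumed: ED day uniform over Days 2–360, the five visit offsets equally likely, and the scheduled visit attended.

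**Example.** Month 3 visit on Day 91, no ACLF; ED visit on Day 100, ACLF. Both fall in Days 77–106. Distances from target are 0 and 9, so the Day 91 negative is used. The ED result enters no other window, so the subject is not counted at 3, 6 or 12 months.

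**Share of ED days unused.** An ED visit before the scheduled visit is normally the only value in its window and is kept. With the scheduled visit at offset o, the unused ED days in a window number (days after target) − |o|. The mean of |o| over −2 to +2 is 1.2.

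| Window | Days in window | Days after target | Mean days unused |
|---|---|---|---|
| Day 11 | 20 | 10 | 8.8 |
| Month 1 | 25 | 15 | 13.8 |
| Months 2–11, each | 30 | 15 | 13.8 |
| Month 12, to Day 360 | 14 | 0 | 0 |

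- Total unused: 8.8 + 13.8 + 10 × 13.8 = 160.6 of 359 days = 44.7%.
- All visits exactly on target: (10 + 15 + 150) / 359 = 48.7%.
- 20% of last scheduled visits missed: 0.447 × 0.8 = 35.8%. With 50% missed: 22.4%.
- Front-loaded discontinuation (exponential, mean 60 or 120 days): 42.4% or 44.1%.
- In a further 4.1% of cases the ED result replaces the scheduled one, which could displace a positive scheduled finding.

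**ED assessments unused, if all 82 dropouts attend an ED visit**
- Whole year: 82 × 160.6 / 359 = 36.7.
- By Day 182: 8.8 + 13.8 + 4 × 13.8 + 0.2 = 78.0 days; 82 × 78.0 / 359 = 17.8.
- By Day 92: 8.8 + 13.8 + 13.8 + 0.2 = 36.6 days; 82 × 36.6 / 359 = 8.4.

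(The 0.2 is Day 92 or 182 itself, unused only when the scheduled visit fell exactly on target, one offset in five.)

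**Events lost, for assumed shares of these assessments showing a first ACLF**

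| Share (assumed) | By Day 92 | By Day 182 | Whole year |
|---|---|---|---|
| 5% | 0.4 | 0.9 | 1.8 |
| 10% | 0.8 | 1.8 | 3.7 |
| 20% | 1.7 | 3.6 | 7.3 |
| 30% | 2.5 | 5.3 | 11.0 |

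The largest entry is 11.0 / 410 = 2.7 percentage points.

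**Between-arm shift.** With assumed dropout of 25% and 15% in the two arms, the shift is 0.10 × 0.447 × share: 0.4 points at 10% and 1.3 points at 30%. The standard error of the difference at an assumed 30% incidence is √(2 × 0.3 × 0.7 / 205) = 4.5 points.

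**The case against.** The best counter-argument comes from SAP 9.3.1 itself. It refers to all evaluations through Month 12 and counts both Day 11 and Month 1 findings as Month 1, which reads like a count over every assessment. The separate by-visit grade table could explain why ACLF appears in Appendix 4. This stands in part: a programmer could reasonably read 9.3.1 as overriding the window rule. But the SAP does not say so, and 6.1.5 covers exploratory endpoints and applies for each parameter. The two texts therefore conflict, and either reading needs a clarifying sentence.

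Four stronger readings are tempting but not supported:

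- *ACLF events will be deleted.* That follows only on the literal reading and only when the scheduled visit in the same window was attended. All evaluations remain in the listings.
- *The discarded visit is when ACLF is most likely.* The documents give no such rate. Protocol 5.3.3 allows withdrawal for reasons such as subject request or inclusion error.
- *The whole-year loss applies at each time point.* It is smaller at 3 and 6 months. Not every planning dropout need have an ED visit either: Protocol 5.3.5 ties it to receipt of study product (SAP 5.2.5 is broader), and under Protocol 5.3.2 transplant recipients and subjects stopping treatment for listed severe adverse events continue planned visits.
- *The time limits in SAP Section 9 and Appendix 4 contradict each other.* The Section 9 table is introduced with "For the purposes of defining the analysis period for each of the efficacy analysis timepoints the following will be applied", but its cut-off dates are invoked as censoring dates in the time-to-event sections. SAP 9.3.1 works in visit months and cites no date. The upper limit for ACLF is unstated rather than contradictory.

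**Conclusion.** The point holds as an unreconciled conflict. An any-occurrence endpoint sits under a one-value-per-window rule that, applied literally, drops ACLF first seen at an ED visit after an attended scheduled visit in the same window. About 45% of ED assessments would go unused with uniform ED days and visits attended within ±2 days, and 22% to 36% if 50% or 20% of last visits are missed.

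The number of events lost cannot be derived from the documents. The illustrations rest on assumed ACLF rates and full ED attendance, and the between-arm shifts calculated are well below the standard error. The case for a change is that subjects with an observed event could be misclassified; a reversed conclusion is not shown to be likely. ACLF incidence is exploratory and outside the fixed testing sequence of SAP 6.5, so no primary or secondary test is affected.

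**What to change.** Add to SAP 9.3.1:

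- The one-value-per-window rule of 6.1.5 does not apply to the any-occurrence ACLF endpoint.
- ACLF counts at any post-baseline scheduled visit by its CRF label (Day 11 through Month 3, 6 or 12) and at any ED visit by its actual date.
- The upper limit for each period is stated, and it does not exclude scheduled visits within their ±2-day window.

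The last item matters. The Section 9 cut-offs of randomization + 91, + 181 and + 361 days are Days 92, 182 and 362 when randomization is Day 1. Applied to every assessment, they would exclude compliant visits on Days 93, 183 and 363. A date limit also settles the example: with a limit at Day 92, the Day 100 finding would count at 6 and 12 months but not at 3.

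For ACLF, keep the Appendix 4 windows and the nearest-to-target rule for the by-visit grade summary only. The cost is a few sentences in the SAP and a small programming change, with no new data.

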6.1.6 Adverse Events

Adverse events will be classified as TEAEs or non-Treatment-Emergent AEs (non-TEAEs), based on the comparison of the AE onset date/time with the start date/time of study treatment. For the SMT + Albutein 20% treatment group, TEAE is defined as an AE occurring during or after the first Albutein dose administration. For the SMT treatment group, it is assumed that subjects were already receiving SMT per institutional standards at the time of randomization; therefore, a TEAE will be defined as an AE occurring at or after randomization.

A non-TEAE will be defined as an AE which starts during screening and prior to the start of the first administration of study treatment in the SMT + Albutein 20% treatment group. For the SMT group, a non-TEAE is an AE that starts during screening and prior to randomization.

An AE with incomplete start date/time will be determined to be a TEAE or non-TEAE using the conservative rule specified in [Appendix 2](#).

Any AE with a missing end date will be considered ongoing.

6.1.7 Prior and Concomitant Medications and Blood Products

Prior (within 30 days prior to screening) and concomitant medications were required to be recorded in the eCRF. Prior medications and concomitant medications will be summarized separately either overall and by treatment (prior medications) and by treatment group (concomitant medications).

GRIFOLS	Bioscience Industrial Group	Number	BIG-CL-SP-000319	Version	2.0	Status	Effective	Effective Date	09-Sep-2024	Page	21 of 52
		IG1601	Statistical Analysis Plan								

Prior medications are defined as any medication that ended with end date/time prior to the start of study treatment (i.e., start of the infusion for the SMT+ Albutein treatment group, or end date/time prior to randomization for the SMT group).

Concomitant medications are defined as medications with start date / time on or after the subject's date / time of randomization (for the SMT group) or commencement of Albutein (SMT+ Albutein treatment group). In addition, medications with start date / time prior to subject's date / time of randomization for the SMT group or commencement of Albutein for the SMT + Albutein treatment group, and end date/time either ongoing or after subject's date / time of randomization for the SMT group or commencement of Albutein in the SMT + Albutein treatment group will also be deemed as a concomitant medication.

Prior and concomitant blood products are defined in the same manner.

The following conservative imputation rules will be used for missing or partial end date / time information in order to determine whether a medication is prior or concomitant (i.e., the unknown portions of a medication end date / time will be assumed to be as late as possible):

- Note: year is required on the eCRF, except for ongoing medication
- If the entire end year, date and time values are missing (i.e., ongoing medication), then no imputation is performed, and the medication will be assigned to the “concomitant” category
- If the month is missing, impute “December”
- If the day is missing, impute the last day of the month (i.e., “28/29/30/31” depending on the year and month)
- If the hours are missing, impute “23”
- If the minutes are missing, impute “59”

The imputed medication end date / time will then be compared with the start of study treatment to determine if the medication is prior or concomitant. Note: it is possible that the imputed end date / time could be assigned to be later in time than the data lock.

Note the imputed end date / time will only be used to determine whether a medication is prior or concomitant. The start / end dates / times reported on the eCRFs will be presented in the listings.

6.2 Sample Size

Based on the CANONIC study, the overall 1-year transplant-free mortality rate in the current study population is assumed to be about 46% (11,16). Assuming a potential drop-out rate of 20% and 5% type-1 error for a 2-sided Chi-square test, a global sample size of 410 patients (205 per treatment group) will allow an 80% statistical power to detect an absolute reduction of 15% (17) for the 1-year mortality rate in subjects treated with SMT + Albutein 20%.

GRIFOLS	Number	IG1601	Version	2.0	Status	Effective	Effective Date	09-Sep-2024	Page	22 of 52
BIG-CL-SP-000319 IG1601 Statistical Analysis Plan										

GRIFOLS	Number	BIG-CL-SP-000319		Version	2.0	Status	Effective	Effective Date	09-Sep-2024	Page	23 of 52
	IG1601 Statistical Analysis Plan										

Alternatively, the sample size was calculated based on the log-rank test as follows. Assuming the 1-year transplant or mortality rate is 46% for the control group, or equivalently, the transplant-free survival rate is 54%, which translates to a hazard rate of 0.0017 assuming an exponential distribution. Using a log-rank test at the 2-sided significant level of 5%, a total of 125 events would provide at least 80% power to detect an absolute reduction of 15% in transplant or mortality rate (a 31% 1-year transplant or mortality rate, or equivalently, a 69% transplant-free survival rate) in subjects treated with SMT + Albutein 20%. This absolute difference in transplant or mortality rates translates to a hazard ratio of 0.6022, or an approximate 40% risk reduction. With all subjects followed for the entire 1-year duration of the study, a total of 322 subjects would be required to obtain 125 events. Assuming a dropout rate of 20%, a global sample size of 404 subjects (202 per treatment group) is required. This sample size calculation was performed using Proc Power with the two-sample survival statement in SAS version 9.4.

Taking a conservative approach, the larger of the 2 sample sizes (i.e., 410 subjects based on the Chi-square test) will be used to ensure the study has sufficient power.

6.3 Randomization and Blinding

This is an open-label study. Subjects will be randomized into one of two groups (SMT + Albutein 20% versus SMT alone) in a 1:1 ratio based on a computer-generated randomization schedule. Randomization of subjects will be stratified by region (Europe or North America) and by whether or not subjects have been previously hospitalized for acute decompensation of liver cirrhosis prior to the most recent hospitalization for acute decompensation of liver cirrhosis with ascites as required by Inclusion Criterion #3v4. Within each stratum (i.e., each unique combination of region and history of hospitalization for acute decompensation of liver cirrhosis), eligible subjects will be randomized in a 1:1 ratio into 1 of 2 treatment groups.

6.4 Analysis Populations

6.4.1 Safety Population

The Safety Population is defined for the SMT + Albutein 20% as the subset of subjects who receive any amount of Albutein 20% treatment while on SMT, and is defined for the SMT alone treatment as all subjects randomized to SMT, assuming that all subjects in the SMT arm received the SMT treatment. The Safety Population will be used for all safety analyses. Subjects will be grouped according to the treatment they actually received in all safety analyses.

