8.3.11 Reporting of Serious Adverse Events, Deaths, and Pregnancy

8.3.11.1 Reporting of Serious Adverse Events

Any SAE (see Section 8.3.7) that occurs after signing the study ICF through the Final Visit (ie, End of Study or Early Discontinuation Visit) must be expeditiously reported whether or not considered attributable to the study drug. Each SAE must be fully recorded in the subject's eCRF and SAE Report Form. In addition, any SAE that occurs after the end of study/early discontinuation should be reported if the investigator feels that the event is related to the use of IP.

SAEs will be reported using the designated SAE Report Form. When the investigator becomes aware of an SAE, she/he must submit a completed, signed, and dated SAE Report Form (in English) within 24 hours to the sponsor by email/fax. The date of this SAE discovery by the study center staff should be documented in the source documents (ie, medical records).

Each SAE must be followed up until resolution or stabilization. After the initial report, all relevant information for SAE follow-up, and for the outcome, must also be supplied to the sponsor in a timely manner (within 3 days from its identification or within 24 hours for relevant new information) by means of the SAE Report Form. In addition, the sponsor or contract research organization may request additional information and/or reports.

All SAE Report Forms must be reported to:

When required, and according to local law and regulations, SAEs must be reported to the IRB/EC and regulatory authorities. Copies of the investigator's reports must be sent to the sponsor.

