9.1.3.1 Adverse Events

Adverse events will be coded and classified using MedDRA[®] terms (system organ class and preferred terms).

When a causal relationship of an AE is classified by the investigator as definitively or possibly related, the event will be defined as a suspected ADR. A suspected ADR with a causal relationship of "definitively related" will be defined as an AR. The sponsor will consider the investigator's causality assessment and also provide its own assessment. If there is any disagreement in the causality assessment between the investigator and the sponsor, a separate summary of suspected ADRs/ARs will be provided.

For summary purpose, AEs will be classified as treatment-emergent AEs (TEAEs) or non-TEAEs depending on the comparison of AE onset date/time with the start date/time of study treatment. A TEAE will be defined as an AE which occurs between the start of study treatment and the final visit of the clinical study. A non-TEAE will be defined as an AE which occurs prior to the start of study treatment. Non-TEAEs and TEAEs will be summarized separately.

In addition, TEAEs, including suspected ADRs, will be summarized by each treatment group, system organ class, preferred term, causal relationship, severity, and seriousness (serious versus non-serious) using descriptive statistics. At each level of summarization, a subject will only be counted once per system organ class or preferred term using the most severe AE or the AE with the strongest causal relationship to the treatment.

AEs temporally associated with the infusion of the IP (ie, infusional AEs, including infusional suspected ADRs) will be summarized by presenting infusion/subject incidences and percentages and listed.

Subjects with SAEs, AEs leading to death, or who withdraw from the study because of an AE will also be individually listed and summarized.

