9.7 Subject Population for Analysis

There will be 3 analysis populations in this study; 2 populations for efficacy assessment and 1 population for safety evaluation.

The ITT population is defined as all subjects who are randomized. The ITT population will be used for all efficacy analyses. Subjects will be grouped according to the treatment to which they are randomized in all efficacy analyses.

The PP population is defined as the subset of subjects included in the ITT population who do not present major protocol violations which might have an impact on the primary efficacy analysis, complete at least 80% of the scheduled treatments and are not excluded from the study for interrupting the Albutein 20% treatment for more than 4 consecutive weeks (SMT + Albutein 20% treatment group subjects). The primary efficacy analyses will be carried out using the PP population in order to confirm the results based on the ITT population.

The Safety population is defined as the subset of patients who receive at least one SMT plus Albutein 20% treatment or SMT. Safety analyses will be based on this population. Subjects will be grouped according to the treatment they actually received in all safety analyses.

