with onset date/time on or after the subject's randomization date/time for SMT arm, and with onset date/time during or after the first dose administration for the SMT + Albutein 20% arm. For subjects in the SMT + Albutein 20% arm, the first dose is scheduled on the same day as randomization. The definition is modified because the treatment time after randomization entered in the EDC for subjects in the SMT arm may not be on day 1, which may cause bias in the comparison of TEAE between the two groups. The new definition assumes that subjects in the SMT group had been on the SMT treatment before entering the trial. The new definition intends to remove bias in the comparison of TEAE between two treatment groups.

Changes in the analysis of longitudinal outcomes

The MMRM will be used to analyze the longitudinal continuous outcomes [e.g., CLIF-C OF score, CLIF-C ACLF score, CLIF-C AD score, MELD score, EQ-5D-5L index score, EQ-5D-5L VAS score], and general linear model implemented in SAS Proc GENMOD will be used to analyze the longitudinal binary or ordinal outcomes [Child-Pugh Score, Incidence of disease-related complications, Incidence of insertion of TIPS for refractory ascites]. However, as stated in Section 9.1.2.3 of the protocol, exploratory endpoints would be analyzed by means of ANCOVA or Student's t tests (for normally-distributed variables), non-parametric Mann-Whitney U test (for non-parametric variables), and Fisher's exact test or Chi-square test (for binomial variables). The methods specified in the protocol are not suitable for longitudinal outcomes with missing data.

Adding Ethnicity as a new subgroup analysis

The Ethnicity is collected in EDC. To account for any possible differential treatment effect based on ethnicity, a subgroup analysis will be done comparing Hispanic subjects vs non-Hispanic subjects. This subgroup analysis is incorporated in the appropriate sections above (see [Section 9.1.4](#)).

GRIFOLS	Number	BIG-CL-SP-000319	
	Version	2.0	
	Status	Effective	
	Effective Date	09-Sep-2024	
	Page	46 of 52	

13 References

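### The SAP's Safety population requires an infusion on Albutein but only randomization on SMT, and its TEAE window starts differently by arm with no stated end, so the between-arm TEAE, SAE and fatal-TEAE tables do not compare like with like

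*SAP*

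**What the plan says.** **Subject sets.** Protocol 9.7 states: "The Safety population is defined as the subset of patients who receive at least one SMT plus Albutein 20% treatment or SMT". SAP 6.4.1 gives each arm its own rule. For Albutein it is "the subset of subjects who receive any amount of Albutein 20% treatment while on SMT". For control, the population "is defined for the SMT alone treatment as all subjects randomized to SMT", with receipt of SMT assumed. The same SAP section adds: "Subjects will be grouped according to the treatment they actually received in all safety analyses". The opening of SAP Section 10 bases all safety listings and summaries on this population unless otherwise noted.

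**Windows.** Protocol 9.1.3.1 states: "A TEAE will be defined as an AE which occurs between the start of study treatment and the final visit of the clinical study". SAP 6.1.6 says that for the Albutein arm "TEAE is defined as an AE occurring during or after the first Albutein dose administration"; for SMT the start is randomization. Neither SAP rule gives an end. SAP Section 12 discloses the changed TEAE definition and gives its purpose: "The new definition intends to remove bias in the comparison of TEAE between two treatment groups".

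**After the final visit.** Protocol 8.2.1 and 8.3.8 close AE collection at the End of Study or Early Discontinuation Visit in both arms. Protocol 8.3.11.1 then adds that "any SAE that occurs after the end of study/early discontinuation should be reported if the investigator feels that the event is related" to the product.

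**The concern.** Protocol 9.1.3 bases the safety comparison on reading descriptive tables side by side. No model adjusts for unequal subject sets or unequal windows, so the definitions themselves must be comparable.

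The trial is open-label, so allocation is known before the first infusion. Protocol 5.3.3 allows withdrawal on request or for an inclusion error. A subject who deteriorates or leaves between randomization and first infusion is lost from the Albutein column. The same subject on SMT stays in. If such subjects carry more events than average, the Albutein column looks safer than it is. The missing end of the window works the other way, because it can add product-attributed SAEs to the Albutein column alone.

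**Working it through.** **1. Where a never-infused Albutein subject goes.**
- Protocol 9.7: the subject received SMT, so belongs to the Safety population and, by treatment received, sits in the SMT group.
- SAP 6.4.1: the subject received no Albutein, so fails the Albutein rule; the subject was not randomized to SMT, so fails the SMT rule. The as-treated sentence groups members of the population and does not admit anyone to it.
- Result: the subject is in neither set, and the AEs leave the safety listings as well as the tables. SAP Section 12 explains the TEAE change but not this one.

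**2. The plan's own figures, used only for scale.** Inputs from SAP 6.2: 46% against 31%, two-sided 5%, 80% power, 20% dropout. With pooled proportion 0.385, n per arm = [1.960 × √(2 × 0.385 × 0.615) + 0.842 × √(0.46 × 0.54 + 0.31 × 0.69)]² / 0.15² = 164.0. At 164 per arm the power is 0.79998, and 164 / 0.8 = 205, the stated arm size. The control hazard is −ln(0.54) / 365 = 0.00169 per day, matching the stated 0.0017.

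**3. Effect of dropping never-infused subjects.** Let k be the number never infused, r their risk and p the arm's overall risk. The Albutein percentage becomes (205p − kr) / (205 − k), a shift of −k(r − p) / (205 − k). The documents do not give k or r, so both are assumptions. I take p = 46%, the planning rate for death or transplant, as a stand-in background, with 205p = 94.3.

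| k (share of 205) | r = 46% | r = 70% | all had the event |
|---|---|---|---|
| 2 (1%) | 0 | −0.24 | (94.3 − 2)/203 = 45.47%, −0.53 |
| 4 (2%) | 0 | −0.48 | (94.3 − 4)/201 = 44.93%, −1.07 |
| 10 (5%) | 0 | −1.23 | (94.3 − 10)/195 = 43.23%, −2.77 |

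Shifts are in percentage points. At a lower background the last column grows, but it cannot exceed k/205: 1.0 point for k = 2 and 4.9 points for k = 10, reached only if the never-infused subjects supplied every event in the arm.

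**4. Effect of the start gap.** Expected deaths or transplants among 205 at the control hazard are 205 × (1 − exp(−0.00169 × days)): 0.09 in 6 hours, 0.35 in 1 day, 1.04 in 3 days. SAP 6.1.2 schedules the first infusion for the day of randomization, so the first figure is the relevant one unless dosing was delayed.

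**5. Effect of the missing end.** After the final visit only SAEs judged related to the product are requested. SAP 5.4.2 says that ADRs do not apply to SMT. Any such SAE therefore falls in the Albutein column. The documents give no basis for a count.

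**6. Where to put the never-infused subjects.** Take k = 10, all with events, and a true risk of 46% in both arms.
- SAP rule: 84.3/195 = 43.2% against 94.3/205 = 46.0%, a spurious gap of 2.8 points.
- Protocol rule (moved to the SMT column): 43.2% against 104.3/215 = 48.5%, a spurious gap of 5.3 points.
- By assigned arm: 46.0% against 46.0%, no gap.

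**The case against.** The best case for the plan has five parts.

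- **The start difference is planned, disclosed and small.** The protocol already started TEAEs at study treatment, so the infusion clock on Albutein is not new; the SAP changed the SMT start and says why. Pre-infusion AEs in infused subjects still appear in the SAP 10.1 category for onset before treatment. This stands, and the start gap is a minor part of the point.
- **The open end is not specific to Albutein.** A reader might infer that the SAP left the window open for Albutein alone. It states no end for either arm, and routine AE collection stops at the same visits in both. What is one-sided is only the later reporting of product-related SAEs, which comes from the protocol and counts against Albutein.
- **Deaths are not lost.** A reader might infer that early deaths vanish from the comparison. They do not: SAP 9.2.1, 9.2.3 and 9.2.5 compare all-cause death in the ITT population from randomization. Only the table of TEAEs leading to death is affected.
- **Much early deterioration is outside the AE tables anyway.** Protocol 8.3.3.1, 8.3.10 and 8.3.11.2 keep anticipated disease progression, and deaths unequivocally due to it, out of AE and SAE reporting unless the product is suspected. This limits the size of the effect in both arms.
- **The protocol text can be read arm by arm.** The synopsis wording of the Safety population lends itself to that reading, which would make the SAP less of a departure. Even so, the SAP's rule leaves the never-infused subject unplaced.

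None of this answers the population gap itself, which stands.

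**Conclusion.** The Safety population and the TEAE start are defined differently by arm, and the window has no stated end. The TEAE, SAE and fatal-TEAE tables therefore compare infused Albutein subjects from first dose with all SMT subjects from randomization. The population part is the main one, and it is unrecorded.

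Its size rests on the number never infused, which the documents do not give. Under the assumed 1-5% and a 46% background, the shift runs from zero (risk equal to the background) to about 0.5-2.8 points (all had the event). A clear net bias in favour of Albutein might be inferred, but the documents do not support it: the direction of the exclusion depends on the unknown risk of those excluded, and the late product-related SAEs push the other way.

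Restoring the protocol's as-treated population might also look like the remedy. It is not, because it moves the excluded subjects' events into the SMT column and in the extreme case widens the spurious gap from 2.8 to 5.3 points. The change is worth making because it is cheap and removes an avoidable imbalance; efficacy conclusions do not depend on it.

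**What to change.** 1. For between-arm tables, count AEs from randomization to the final visit (End of Study or Early Discontinuation) in both arms.
2. List SAEs reported after the final visit separately.
3. Repeat the SAE and fatal-AE tables for all randomized subjects by assigned arm. Do not place never-infused Albutein subjects in the SMT column.
4. Report the number randomized to Albutein and never infused.
5. Record the Safety population change, with its reason, in SAP Section 12.
6. Keep the first-infusion clock for Albutein-only tables: suspected ADRs, infusional AEs and rates per infusion.

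The cost is SAP wording and repeated SAE and fatal-AE tables. The downside is small: a few pre-infusion events will appear in the Albutein column of the between-arm tables.
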